### 3.2.3.3.1 Center of Gravity Deviation

The student participant completes a 360° rotation around the axis of one leg, with the other leg off the ground, and maintains static balance. During the test, the student participant must keep the torso stable during high-speed rotation to avoid imbalance caused by the deviation of the center of gravity. To assess performance, the three-dimensional displacement of the center of mass is tracked via an Inertial Measurement Unit (IMU), and the overlap degree between the actual trajectory and the ideal path is calculated using the formula

$D = \sqrt{(X \text{ real} - X \text{ ideal})^2 + (y \text{ real} - y \text{ ideal})^2 + (Z \text{ real} - Z \text{ ideal})^2}$  ; smaller values indicate higher neuromuscular coordination and stronger action stability (Farana et al., 2023).

The Vicon high-speed camera system (200 Hz) captures the movement trajectory, and center of mass deviation is calculated in combination with an inverse dynamics model, while ground reaction force is measured by a Force Plate (sampling rate 1 kHz) to provide biomechanical validation of balance control (Karatsidis et al., 2019).

### **3.2.3.3.2 Body Oscillation Amplitude (m)**

During the dynamic single-leg support rotation, student participants are required to maintain the other leg completely off the ground while keeping the spine in a stable neutral position, with measurements taken for the maximum lateral/longitudinal displacement of the torso and lower limbs (e.g., lateral sway of the upper body during rotation). This assessment evaluates core stability by reflecting the anti-interference capability of deep core muscle groups (e.g., transversus abdominis, multifidus) against rotational centrifugal force (Vasseljen et al., 2012). The oscillation amplitude serves as an action economy indicator, with a positive correlation to energy consumption—optimizing this parameter can enhance movement efficiency, as described by the theoretical model  $E_{loss}=k \cdot A^2$  (where A represents oscillation amplitude). Using high-speed photography ( $\geq 200$  Hz), movement trajectories are captured and combined with a rigid body dynamics model to calculate three-dimensional oscillation amplitudes. Insufficient activation of core muscles, as noted by Gribble et al., 2012, often leads to compensatory excessive abduction/adduction of the hip joint, highlighting the neuromuscular mechanisms underlying rotational stability.

### **3.2.3.3.3 Rotation Smoothness Index (°)**

During the evaluation of an athlete's momentum coherence from the starting position to completing a  $360^\circ$  rotation—characterized by uniform rotation without deceleration or acceleration phases—the participant must maintain natural hanging of the upper limbs and avoid torso twisting as key action requirements (Fukata et al., 2025). A smoothness index (SI)  $> 85^\circ$ , a benchmark for professional athletes, indicates optimal movement quality, while an SI  $< 70^\circ$  signals muscle coordination disorders (e.g., mismatched force generation between the hamstrings and gluteus maximus). This metric correlates positively with rotational speed and landing stability, as described by the theoretical model  $v = \frac{2\pi \cdot R}{T}$  (where T is the rotation

period) (Kuo & Donelan, 2010). To quantify movement smoothness, the joint angular velocity curve is analyzed via Fourier transform using the formula  $SI = \frac{1}{T} \int_0^T |\dot{\theta}(t)| dt$ , which captures deviations from uniform rotation. Neurologically, the cerebellum-basal ganglia loop regulates movement rhythm; abnormal neural discharges within this circuit can disrupt speed consistency, highlighting the neuromuscular mechanisms underlying rotational control and competitive performance optimization (Taiar et al., 2022).

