### **1.3 RESEARCH QUESTIONS**

- (1) What are the differential effects of static, dynamic, and static-dynamic combined balance training on the stability (measured by the maximum distance of single-leg extension and the bilateral symmetry index in the Star Excursion Balance Test (SEBT)) of beginner gymnasts?
- (2) Do static, dynamic, combined balance training induce distinct improvements in jumping mechanics (CMJ/SLCMJ: jump height, PF, RFD, impulse) and kinetic efficiency (jump height/GRF ratio), and does combined training show superior neuromuscular adaptations?
- (3) Among static, dynamic, and static-dynamic combined balance training modalities, which one most effectively minimizes the center of mass (COM) offset distance, body sway amplitude, and landing impact force—while maximizing rotational smoothness and single-leg balance duration—in beginner gymnasts when they perform 360° single-leg standing pirouettes and 360° straight-body jump turns, with all outcomes quantified by 3D motion capture technology?

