#### **1.4.2 Specific objective**

- (1) Evaluate the effects of static balance training, dynamic balance training, and combined static-dynamic balance training on the stability of beginner gymnasts. Quantify the maximum single-leg extension distance (reflecting lower limb support force) and the bilateral symmetry index (reflecting neuromuscular coordination) through the SEBT test to compare the differential effects of different training modes on stability improvement.
- (2) To evaluate the effects of static balance training, dynamic balance training, and combined static-dynamic balance training on the jumping skills of beginner gymnasts, this study measures the changes in data (such as jumping height, peak force, rate of force development, and impulse) of athletes during countermovement jump (CMJ) and single-leg countermovement jump (SLCMJ) before and after training. Through these measurements, it

aims to deeply analyze the mechanism of action of different training modes in enhancing the jumping ability of beginner gymnasts.

(3) This study aims to explore the improvement effects of static balance training, dynamic balance training, and combined static-dynamic balance training on the performance of gymnastic movements (such as standing 360° single-leg turn and straight jump 360° turn). Through three-dimensional motion capture technology, the study assesses beginner gymnasts in terms of center of gravity deviation distance, body oscillation amplitude, rotation smoothness index, and landing impact force during the standing 360° single-leg turn. For the straight jump 360° turn, it conducts quantitative analysis based on center of gravity deviation distance, joint angle variation, vertical jump efficiency, and landing impact force.

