Impulse:	In countermovement jumps, impulse is the accumulation of ground reaction force (GRF) over time (the area under the force-time curve) (Claudino et al., 2017). Its net impulse (total impulse minus gravitational impulse) determines the change in human momentum, directly dictating the takeoff velocity and jump height (Painter et al., 2022).
Center of gravity deviation distance	In rotational movements, the center of gravity deviation distance refers to the perpendicular deviation distance of the center of gravity (CoG) relative to the rotation axis—the smaller the deviation, the higher the efficiency of rotational control (Lee et al., 2021).
Joint Angle variation	It refers to the dynamic angular changes in each joint relative to the initial posture, which regulates the moment of inertia and angular momentum by adjusting joint flexion/extension to achieve precise control over rotational speed and stability (Moke et al., 2020).

Vertical Jump Efficiency	It refers to the ability to convert energy generated by muscle contraction (especially the elastic energy stored during the eccentric-concentric contraction cycle and the energy from active force generation) into the gravitational potential energy required for the vertical displacement of the body's center of mass (Kazuaki et al., 2022).
Landing Impact Force	It refers to the instantaneous peak force generated by the ground reaction force (GRF) now the body contacts the ground (Mojaddarasil & Sadigh, 2021a).
Body Oscillation Amplitude	It refers to the maximum displacement of the body's center of mass (or specific segments) relative to the equilibrium position during dynamic movements such as running, jumping, and walking (Pettorossi et al., 2013).
Rotation Smoothness Index	It is a quantitative index used to evaluate the smoothness of the angular velocity time series in rotational movements (such as gymnastic twists and figure skating spins) (Sjölander et al., 2008).

## CHAPTER 2

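### The Rotation Smoothness Index as printed is a mean angular speed, so its formula does not match its stated meaning, unit, scoring direction or cut-offs

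*Protocol*

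**What the plan says.** Section 1.6 defines the outcome: "It is a quantitative index used to evaluate the smoothness of the angular velocity time series in rotational movements". Section 1.4.2 lists it among the single-leg turn outcomes ("body oscillation amplitude, rotation smoothness index, and landing impact force during the standing 360° single-leg turn"), and section 1.3, question 3, asks which training mode is best at "maximizing rotational smoothness and single-leg balance duration". Table 20 gives it a column, in degrees.

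The formula appears only in section 3.2.3.3.3. The ideal there is "uniform rotation without deceleration or acceleration phases". For the computation, "the joint angular velocity curve is analyzed via Fourier transform using the formula" SI = (1/T) ∫₀ᵀ |θ̇(t)| dt, "which captures deviations from uniform rotation". Scoring runs upward: a value above 85° is "a benchmark for professional athletes, indicates optimal movement quality", and a value below 70° signals a coordination disorder. The section adds: "This metric correlates positively with rotational speed and landing stability".

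On turn speed, section 3.2.3.3 asks for a constant speed but gives no value. Section 3.2.3.3.1 describes the same movement as high-speed. Section 3.8.2.3 has a real-time alert for too low an angular velocity, without a threshold.

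**The concern.** The time average of |θ̇| is a speed. Smoothness concerns how speed varies within the turn, and averaging removes that variation. An outcome built this way could miss a real change in evenness. It could also record a change in turn speed, or added wobble, as better smoothness. Research question 3 asks which arm maximises smoothness, and the protocol gives no other formula for it.

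**Working it through.** **Inputs.** The formula, the 85 and 70 cut-offs and the scoring direction come from section 3.2.3.3.3, and the 360° angle from section 3.2.3.3. The protocol gives no turn duration or speed profile, so those below are assumptions for illustration. It states no numerical result for SI to reproduce.

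**1. Unit.** ∫|θ̇| dt is in degrees. Divided by T in seconds it is in °/s. The section heading, the cut-offs and Table 20 all say °.

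**2. Whole-body angle, no reversal.** If θ̇ ≥ 0 throughout, ∫|θ̇| dt = 360, so SI = 360/T for any profile. This was checked by numerical integration. Each profile has ramps over the first and last 10% of the turn and is scaled to 360°; T = 2.0 s:

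| Profile | SI | CV of angular velocity, 36° to 324° |
|---|---|---|
| Even | 180.0 | 0.000 |
| Uneven (factor 1 + 0.42 sin, 2 cycles) | 180.0 | 0.277 |
| Stop-start (factor 1 + 0.97 sin, 3 cycles) | 180.0 | 0.667 |

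At T = 4.8 s, which puts SI between the two cut-offs, all three score 360/4.8 = 75.0.

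**3. Speed.** A turn shorter by a fraction f raises SI by 1/(1 − f) − 1: 5.3% for f = 5%, 11.1% for 10% and 25.0% for 20%, with evenness unchanged.

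**4. Cut-offs read as °/s.** SI > 85 means T < 360/85 = 4.24 s. SI < 70 means T > 360/70 = 5.14 s. A perfectly uniform turn of 5.5 s scores 360/5.5 = 65.5 and falls in the disorder band.

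**5. Reversal.** With backward rotation b, SI = (360 + 2b)/T. For b = 42.1° and T = 2.0 s, SI = 444.2/2.0 = 222.1, which is 23% above 180.0.

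**6. Joint angle.** The text speaks of a joint angular velocity curve. A 30° flexion and return in 2.0 s gives 60/2.0 = 30.0. With an added 2° oscillation at 4 Hz it gives 39.6 (+32%). The oscillation raises the score, and the section reads a higher score as better.

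**7. A dot lost in PDF reading (θ̈ instead of θ̇).** Mean |angular acceleration| for the three profiles in step 2 is 200, 456 and 1184 °/s². This version does detect unevenness, but the roughest turn scores highest and the unit is °/s².

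**8. Fourier wording.** The formula has no spectral term, so that wording does not change the result.

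**9. Check on the remedy.** For an even turn with ramps fixed at 0.2 s, the CV over the whole turn is 0.308, 0.265 and 0.214 at T = 1.5, 2.0 and 3.0 s. It therefore drifts with duration through the ramps alone. Over 36° to 324° it is 0.000 at each duration.

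**The case against.** Several counter-arguments have force.

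- **Speed dependence is declared.** Section 3.2.3.3.3 says the metric rises with rotational speed. That is so, but section 1.6 defines the index as smoothness of the angular velocity series. A metric that is 360/T for every non-reversing turn measures speed and nothing else. The declaration does not resolve the conflict.
- **The wording alone is not contradictory.** A reader might infer that an index said to capture deviations cannot also be best when high. The text does not support this: an index that falls as deviations grow also captures them. The conflict arises only when the formula is set beside its unit, direction and cut-offs.
- **The index is not useless on every reading.** A reader might conclude that it cannot address research question 3 at all. On the acceleration reading (step 7) it separates even from uneven turns and would serve once unit and direction were corrected.
- **The task is partly controlled.** Section 3.8.2.3 alerts on insufficient angular velocity, and section 3.2.3.3 accepts a trial only without loss of balance or sway. Turn duration is still not fixed, because no speed or threshold is given. The validity rule does mean that a turn with 42° of back-rotation might be rejected, so step 5 shows direction only and is not an expected size.
- **The examples are assumed.** At 2.0 s every whole-body score is more than twice the 85 cut-off. The identity SI = 360/T does not depend on that choice, as the 4.8 s case shows.
- **The cut-offs enter no planned test.** This is correct. Table 20 reports means and SDs with ANOVA, so the cut-offs affect interpretation and not the comparison.

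**Conclusion.** Wrong as written. Taken as printed, SI is mean absolute angular speed in °/s. For a non-reversing whole-body turn it does not respond to unevenness and rises when the turn is faster. For a turn with reversals, or a joint angle with added oscillation, it rises with the extra motion. If a dot was lost in the PDF reading, the index detects unevenness but the printed unit and the higher-is-better rule are wrong. On each of these readings the formula and its stated unit, direction and cut-offs cannot all stand.

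Because turn duration is not fixed, a change in turn speed could register as a change in smoothness. A reader might go further and infer that the arms will be ranked wrongly. The protocol does not support that, since nothing in it shows that the arms will differ in turn duration.

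The reach is limited. SI is one of the eight variables in Tables 19 and 20, it is not named primary, and the sample size does not rest on it. The correction should be made before data collection. The result in step 2 follows from the formula alone; only the sizes quoted for particular profiles rest on assumed durations and shapes.

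**What to change.** Before data collection, in section 3.2.3.3.3 and Table 20:

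- Replace SI with a speed-normalised measure of unevenness of whole-body (pelvis) angular velocity, lower meaning smoother. One example is its coefficient of variation over a pre-defined window that excludes the start and stop ramps, such as 36° to 324° of cumulative turn. A normalised jerk measure is an acceptable alternative.
- State which angle θ is, and amend the wording that starts the assessment at the starting position so that it matches the window.
- Report turn duration as a separate variable.
- Correct the unit and the scoring direction, and remove the 85° and 70° cut-offs.

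The cost is a text change: one outcome definition and one table heading. Section 3.2.3.1 already plans pelvis markers and 200 Hz capture. The downside is that values can no longer be set against the quoted benchmarks, and the start and stop phases are not scored.

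Separately, and not in support of this point: section 3.2.2.2 computes countermovement jump height by impulse-momentum and section 3.8.2.1 by flight time. These should be reconciled to one method for both visits.

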### 3.2.3.3.4 Landing Impact Force (N)

After a 360° rotation, vertical impact force at landing is measured with requirements for slightly bent knees and ankle cushioning. An impact force < 1000 N signals high lower limb cushioning efficiency, reducing Achilles tendon injury risk (model:  $F_{buffer} = \frac{mgh}{t^2}$ ). Research shows impact force negatively correlates with the coordination of take-off height and rotation speed (Green, 2006).

Using an impact sensor, peak vertical force is recorded, and cushioning efficiency is calculated via  $Efficiency = \frac{F_{max} - F_{avg}}{F_{max}}$ . Stiffer hamstring-gluteus muscles correlate with lower impact force, offering a basis for technique optimization and injury prevention by linking force measurements to muscle function (Mojaddarasil & Sadigh, 2021b).

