### 3.2.3.3 Measurement of Standing Single - leg 360° turn

Participants assume a split stance position with the front leg flexed at 20–30°, weight evenly distributed over the supporting leg, the corresponding arm extended forward, and the contralateral arm naturally positioned at the side. At the start of the test, using the supporting leg as the axis of rotation, participants complete a 360° horizontal rotation around the vertical axis at a constant speed through coordinated control of the hip joint and core muscles. Throughout the movement, fixed head orientation and gaze direction must be maintained to stabilize the rotational axis, while avoiding trunk flexion, extension, or lateral deviation (Fukata et al., 2025). Upon returning to the starting posture after rotation, the trial is deemed valid if

there is no displacement of the supporting foot, the non-supporting leg does not touch the ground, and no loss of balance or sway occurs, the decomposed movements are shown in Figure 9.

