### 3.8.2.3 TecnoBody 3D Motion Capture System (gymnastic performance movements)

To accurately assess the biomechanical parameters of the 360° straight jump turn and single-leg standing rotation, experimental procedures must integrate standardized protocols with real-time interaction: Test operators first instruct participants to stand still while reflective markers are affixed to anatomical landmarks (acromion, anterior superior iliac spine, greater trochanter, and lower limb joints), emphasizing that "markers must align with bone structures—avoid movement to prevent displacement (Soylu et al., 2025). During static calibration, participants are directed to stand naturally at the center of the force platform with arms relaxed and gaze forward, maintaining stillness for 10 seconds to establish the skeletal model. For formal testing, the straight jump turn requires execution under the command jump vertically, complete a 360° mid-air rotation, and land stably, while the single-leg rotation emphasizes upright posture on the support leg, stable trunk alignment, and 2-second balance maintenance post-rotation, with each movement repeated three times to ensure data reliability. During acquisition, the system provides real-time alerts such as "right knee marker

occluded—adjust arm posture and retest" or "insufficient rotational angular velocity—reduce trunk compensation," ensuring movement standardization. Coaches view screens displaying the participant's center of mass trajectory (red) overlaid with the ideal biomechanical model (green), accompanied by feedback like "0.2-second delay in hip extension—optimize takeoff sequencing." Post-test, data undergoes quality control screening (e.g., center-of-mass deviation standard deviation  $<1.5$  cm, marker occlusion rate  $<5\%$ ), encrypted and stored under the naming convention 'action-date' for subsequent biomechanical modeling and training optimization. This protocol, combining movement standardization, real-time correction, and multimodal data integration, enables granular analysis of rotational techniques (Bravi et al., 2023), supporting technical refinement and injury prevention research in disciplines such as artistic gymnastics and dance.

Figure 13(a) The 3D Motion Capture System

[figure not shown]

Figure 13(b) The Schematic placements of the motion capture system

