#### 4.4.2 Standing Single-leg 360 ° turn test results

Table 20 Standing Single-leg 360 ° turn test results at baseline and 8 weeks postintervention in the static intervention, dynamic intervention, static-dynamic intervention, and control groups. Data presented as mean  $\pm$  SD.

Group	Test Type	Time Point	Center of Gravity Deviation	Body Oscillation Amplitude (mm)	Rotation Smoothness Index (°)	Landing Impact Force (N)	Two-Way Repeated Measures ANOVA	Bonferroni (p)
Static balance group	Standing Single-leg 360 ° turn (Pre-Test)	B						
		W8						
	Standing Single-leg 360 ° turn (Post-Test)	B						
		W8						
Dynamic balance group	Standing Single-leg 360 ° turn (Pre-Test)	B						
		W8						
	Standing Single-leg 360 ° turn (Post-Test)	B						
		W8						
Static and Dynamic balance group	Standing Single-leg 360 ° turn (Pre-Test)	B						
		W8						
	Standing Single-leg 360 ° turn (Post-Test)	B						
		W8						
Control group	Standing Single-leg 360 ° turn (Pre-Test)	B						
		W8						
	Standing Single-leg 360 ° turn (Post-Test)	B						
		W8						

## CHAPTER 5

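### Landing impact force is an outcome of the standing single-leg 360° turn, but a valid trial of that turn contains no landing

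*Protocol*

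**What the plan says.** Objective 3 (section 1.4.2) ends its list of outcomes for this turn with "rotation smoothness index, and landing impact force during the standing 360° single-leg turn". Research question 3 asks which training most reduces landing impact force, and asks it of both the single-leg turn and the straight jump turn. Section 3.2.3.3.4 describes the measurement after the rotation: "vertical impact force at landing is measured with requirements for slightly bent knees and ankle cushioning". It reads values under 1000 N as efficient cushioning, gives the model mgh/t², and relates the force to take-off height. Table 20 gives the outcome its own column in newtons, for all four groups at baseline and week 8.

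The movement itself is defined in section 3.2.3.3. It is a horizontal rotation at steady speed, "using the supporting leg as the axis of rotation". A trial counts only if the supporting foot has not moved, balance is kept, and "the non-supporting leg does not touch the ground". Section 3.2.3.3.1 has the participant turn "with the other leg off the ground, and maintains static balance", and section 3.2.3.3.2 likewise keeps the free leg fully clear of the floor. Section 3.8.2.3 ends the task with "2-second balance maintenance post-rotation".

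Research question 3 also names "rotational smoothness and single-leg balance duration" as quantities to maximise. Balance duration appears neither in Objective 3 nor in Table 20.

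**The concern.** Section 1.6 defines landing impact force as the momentary peak of the ground reaction force when the body meets the ground. In the turn as described, one foot never leaves the ground and the other may not reach it, so the defining event is absent. The sensor will still return a number, and that number will be tabulated and tested as evidence on HA3.

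At stake is one of the four outcomes of this turn. Its group comparison would carry little information on training, and its benchmark would label almost every participant as cushioning well. Alternatively, operators may record some step-down after the turn. They would then be scoring an event that section 3.2.3.3 treats as a failed trial, at a moment that nobody has specified.

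**Working it through.** **1. Is there a landing?** The relevant sections, side by side:

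| Place in Protocol | Support foot | Free leg | Flight or touchdown |
|---|---|---|---|
| 3.2.3.3 | must not move | must not touch down | none described |
| 3.2.3.3.1 | axis of rotation | off the ground | none |
| 3.2.3.3.2 | single-leg support | fully off the ground | none |
| 3.8.2.3 | upright on support leg | – | 2 s hold after the turn |
| 3.2.3.3.4 | – | – | a landing is assumed, with a height and a take-off |

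Four descriptions of the task exclude a landing, and the outcome section presupposes one. For the straight jump turn the position differs: section 3.2.3.2 has a real take-off, flight and landing, and section 3.2.3.2.4 gives it a landing force of its own.

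**2. What would the sensor record?** With the foot planted, vertical force is m(g + a), where a is the vertical acceleration of the centre of mass. In a level, steady-speed turn a is near zero, so the force is near body weight. The Protocol gives BMI 18.5–25 kg/m² (section 3.5.1) but no heights. These are assumed. Body weight is BMI × height² × 9.81.

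- Lower end: 18.5 × 1.55² = 44.4 kg; × 9.81 = 436 N.
- Upper end: 25 × 1.75² = 76.6 kg; × 9.81 = 751 N.
- Wider assumption, 1.50–1.80 m: 408–795 N.

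**3. How far is this from 1000 N?**

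| Peak as multiple of body weight | 1.55–1.75 m | 1.50–1.80 m |
|---|---|---|
| 1.0 | 436–751 N | 408–795 N |
| 1.1 | 480–826 N | 449–874 N |
| 1.3 | 567–976 N | 531–1033 N |

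Reaching 1000 N needs 1000/751 = 1.33 times body weight at the heavy end of the narrower range and 1000/436 = 2.29 times at the light end. The matching upward accelerations are 1000/76.6 − 9.81 = 3.25 m/s² and, with unrounded mass, 12.69 m/s². Nothing in the described movement calls for them.

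**4. The cushioning model.** With no drop, h = 0, and mgh/t² returns 0 N whatever the mass or time.

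**5. Effect on the planned test.** Section 3.6 and Table 20 point to a two-way repeated-measures ANOVA with group, time and their interaction. Suppose the reading is body weight plus noise, and weight is stable. For arms A and B with mean weights W_A and W_B, the interaction contrast is (W_A − W_A) − (W_B − W_B) = 0. The between-arm weight difference W_A − W_B stays only in the group main effect.

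**The case against.** The best defence is that a set-down is intended. Section 3.2.3.3 starts from a split stance and goes back to the opening position. Section 3.2.3.3.4 speaks of knees in the plural and of ankle cushioning. Section 3.2.3.3.2 links the free-leg rule to the rotation phase. On this reading the free foot comes down at the end and its impact is measured. The reading is possible, but it does not remove the conflict: the sentence that returns the participant to the starting posture also voids the trial if the free leg touches down, and no contact event or time window is given. It supports a second way of repairing the text. It does not show that the text is sound.

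Several stronger readings are tempting, and the Protocol does not support them.

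- **Chance weight differences between arms would pass for training effects.** Step 5 shows that stable weight cancels from the interaction, which is the term that reflects differential training. The harm is mainly an uninformative test.
- **Every participant would meet the benchmark, or no effect could ever appear.** A peak force is recorded, and knee bend or heel lowering can add to it. A peak of 1.33 times body weight reaches 1000 N at the upper end of the narrower height range. Moreover, Table 20 reports means and no planned analysis splits at 1000 N.
- **The section was copied from the jump.** It shares the mgh/t² model and mentions take-off height, but it has its own threshold, efficiency formula and sensor. Its origin cannot be known and does not matter.
- **The 2-second hold caps balance duration.** Section 3.8.2.3 requires a hold of that length; it does not say that timing stops there.

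Nor can this be left to a statistical analysis plan. Which physical event is measured, and whether a trial containing it is valid, are matters of protocol definition.

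**Conclusion.** The point stands as an internal contradiction about one outcome of one test. That no landing occurs in a valid trial follows from the Protocol's own definitions and needs no assumption. That the reading would then be mostly body weight is a physical inference for a steady turn on a planted foot. The figure of roughly 436–751 N depends on the assumed heights, and widening them to 1.50–1.80 m does not change the conclusion. The expected loss is one test under HA3 with little information on training and a benchmark that hardly discriminates. No sample-size or power figure depends on it, and the landing force of the straight jump turn is unaffected.

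The absence of balance duration from Objective 3 and Table 20 is a separate, smaller inconsistency with research question 3.

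**What to change.** Remove landing impact force for the single-leg turn from Objective 3, section 3.2.3.3.4 and Table 20. In research question 3, limit it to the straight jump turn, where it should stay.

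If the investigators do intend a set-down, they should instead reconcile sections 3.2.3.3 and 3.2.3.3.4: name the contact event, give the time window in which the peak is taken, and confine the no-touch rule to the rotation and the hold.

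No substitute outcome is needed. Sway during the hold, for example, would overlap with centre-of-gravity deviation and body oscillation amplitude, and section 3.2.3.3 already rejects trials in which sway occurs.

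Separately, align research question 3 with Objective 3 and Table 20 on balance duration, either by deleting it or by defining and tabulating it.

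Dropping the outcome costs some wording and one table column, with no added measurement. The set-down route costs a fuller test definition, settled before baseline testing.
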